8.6. Subsequent Visits

Participants will be reviewed at visits 2, 3 and 4 (3, 6-7 and 11-13 weeks respectively) following sequential, blinded treatment in random order with the study drugs, sildenafil and cilostazol, and placebo for 3 weeks. At each follow up visit they will undergo assessment of potential side effects or unwanted effects (SAEs/SUSARS – see below), including repeat clinical examination and repeat blood tests, as at the baseline visit. Concomitant medications will be recorded, and compliance with study drugs will be assessed by questionnaire and by counting of returned study drug.

Following clinical assessment, the physiological assessment will be repeated as the primary study outcome (pulsatility index). Then the next drug will be dispensed, and any residual drug will be returned.

8.7. MRI Sub-Study

In 60 consenting patients an additional MRI assessment will be performed at each of the follow-up visits on sildenafil and placebo, and up to 30 on cilostazol, to assess cerebrovascular haemodynamics in greater detail. This may involve the following sequences, with a minimum requirement to have FLAIR and SWI images at a minimum of one timepoint and T1, arterial spin labelling and CO₂ reactivity scanning at both timepoints :

At first MRI visit:

- T1 structural image (volume 3D acquisition, 1mm isotropic)
- FLAIR (for quantification of white matter hyperintensities)
- Susceptibility weighted imaging
- Arterial Spin Labelling : 4 vessel selective, non-contrast perfusion imaging (pcASL), to estimate baseline absolute cerebral blood flow
- High frequency, multiband BOLD imaging, optimised for pulsatility of blood flow (pulse-MB, TR 0.4) – 7 minutes monitoring.
- Standard multiband BOLD imaging (according to BioBank imaging protocol) with 5 minutes of fixation on a blank screen, viewing intermittent blank screens then a radial flashing checkerboards.
- Carbon dioxide challenge with inhalation of 6% CO₂ in medical air in 3 minute blocks, interposed with 2 minute blocks of breathing medical air, delivered via an open respiratory circuit with one way valves. Throughout imaging, the participant will have physiological blood pressure, end-tidal CO₂ and oxygen saturation monitoring.

At second / third MRI visits:

- T1 structural image (volume 3D acquisition, 1mm isotropic)
- Diffusion tensor imaging (DTI – 64 directions, for estimation of mean diffusitivity and fractional anisotropy as sensitive measures of white matter injury) (only at second visit)
- Arterial Spin Labelling : 4 vessel selective, non-contrast perfusion imaging (pcASL), to estimate baseline absolute cerebral blood flow
- High frequency, multiband BOLD imaging, optimised for pulsatility of blood flow (pulse-MB, TR 0.4) – 7 minutes monitoring.
- Standard multiband BOLD imaging (according to BioBank imaging protocol) with 5 minutes of fixation on a blank screen, viewing intermittent blank screens then a radial flashing checkerboards.
- Carbon dioxide challenge with inhalation of 6% CO₂ in medical air in 3 minute blocks, interposed with 2 minute blocks of breathing medical air, delivered via an open respiratory circuit with one way valves. Throughout imaging, the participant will have physiological blood pressure, end-tidal CO₂ and oxygen saturation monitoring.

8.8. Sample Handling

All clinical blood tests will be taken for clinical screening and safety purposes and processed via the Oxford University Hospitals NHS Trust laboratory, after which the samples will be disposed of according to local procedures. For research samples, serum, plasma, buffy coat and whole blood samples are prepared and transferred to cryotubes. Each cryotube is labelled with a unique identification number, recorded in the specimen logbook and frozen at -85 °C. All blood samples are stored in freezers in laboratories in the Wolfson Centre for Prevention of Stroke and Dementia

8.9. Discontinuation/Withdrawal of Participants from Study Treatment

Each participant has the right to withdraw from the study at any time. In addition, the Investigator may discontinue a participant from the study at any time if the Investigator considers it necessary for any reason including:

- Pregnancy
- Ineligibility (either arising during the study or retrospectively having been overlooked at screening)
- Significant protocol deviation
- Significant non-compliance with treatment regimen or study requirements
- An adverse event which requires discontinuation of the study medication or results in inability to continue to comply with study procedures
- Withdrawal of Consent
- Loss to follow up

Any data acquired up to the point of withdrawal from the study will be retained except in circumstances where the participant explicitly withdraws consent for this. Participants will not be replaced.

The reason for withdrawal will be recorded in the CRF.

If the participant is withdrawn due to an adverse event, the Investigator will arrange for follow-up visits or telephone calls until the adverse event has resolved or stabilised.

If an individual experiences side-effects on the first treatment, such that they can not continue, they will still be eligible to proceed to the next stage. Similarly, if patients are unable to tolerate study procedures related to secondary study outcomes (ie CO₂ reactivity testing or MRI imaging), they will be able to continue with the study for the purposes of the primary outcome measures (TCD pulsatility index) but not undergo the non-tolerated component. This option will only be provided when the participant expresses a desire to withdraw from the study due to intolerance of the test. If participants withdraw from the study due to clinically significant adverse events, then they will continue to be monitored by the study team until resolution of the adverse event.

8.10. Definition of End of Study

The end of active patient management is the date of the last visit of the last participant (LVLP), but blood will be stored for up to 2 years after LVLP for analysis,

9. INVESTIGATIONAL MEDICINAL PRODUCT (IMP)

9.1. IMP Description

The principal IMP is oral sildenafil, given at 25mg TDS for one week, then automatically increased to 50mg TDS for a further 2 weeks, if tolerated, as determined by its provision in labelled dispensing packs. If side-effects occur at the higher dose, the dose will be returned to the lower dose. Sildenafil is a phosphodiesterase 5 inhibitor, widely used for erectile dysfunction and used in selected patients with primary pulmonary hypertension.

The comparator will be placebo, also taken three times daily.

The secondary comparator IMP is cilostazol, as a positive control, provided at 50mg bd and titrated to 100mg bd after one week, to continue for 2 further weeks. Cilostazol is a phosphodiesterase 3 inhibitor used at this dose in peripheral arterial disease, and used in large randomised controlled Trials of patients with previous stroke, with a beneficial effect compared to aspirin.¹⁹ It is expected to improve cerebral reactivity²² and pulsatility²⁰ and is included as a positive control to assess whether sildenafil has a similar magnitude of physiological effect, to estimate if a sufficient magnitude of clinical effect would be expected, to justify larger clinical trials. In order to preserve the blinding of this study, whilst taking cilostazol twice a day participants will be given placebo to take at midday. This means that, from the participant's perspective, they are always taking the study medication three times daily.

Participants will start sildenafil and cilostazol at lower doses for a week before being titrated up to the high dose. The high dose is similar to the medication's use in usual care, given more frequently in the case of sildenafil, but the titration is necessary to settle the participants on the new medication.

Medications will be overencapsulated, overlabelled and blinded by the Huddersfield NHS Pharmacy Manufacturing Unit, and dispensed by the Oxford University Clinical Trials pharmacy. Medications will be provided in 'dosette' type packaging providing dosing times, such that throughout the study patients will take TDS medication (sildenafil TDS, placebo TDS, cilostazol – placebo – cilostazol). Code-break will be

provided to and retained by the Oxford University Clinical Trials Pharmacy, with individual code-breaking allowed on request of the CI ([name]) when clinically indicated.

For each treatment, medication will be provided as one tablet three times a day for one week, followed by 2 tablets 3 times per day. If side effects occur on the higher dose, the participant will decrease back to one tablet 3 times per day, on discussion with an OxHARP physician. Participants will not be moved on to the higher dose if they are also taking omeprazole due to an interaction with cilostazol.

Labelling and quality control will be performed by Huddersfield PMU according to Volume 4. Good Manufacturing Practices, Annex 13. Manufacture of investigational medicinal products, July 2010.

9.2. Storage of IMP

Medication and placebo will be stored in the Oxford University Clinical Trials pharmacy in recommended conditions, according to pharmacy Standard Operating Procedures. All medications are stable at room temperature for ease of storage by participants.

9.3. Compliance with Study Treatment

Participants will be required to return any unused medications and associated packaging for drug reconciliation at visits 2 and 3. The packaging will incorporate a dosing schedule allowing accurate accounting of compliance.

9.4. Accountability of the Study Treatment

All study medications will be dispensed by the Oxford University Clinical Trials Pharmacy, who will take principal responsibility for drug accountability. Dispensed medications will be documented, and participants will return all study medications to the study pharmacy after each study visit. Number of returned medication will be recorded.

9.5. Concomitant Medication

All concomitant medications will be listed at each study visit. Concomitant use of other PDE5 inhibitors (sildenafil, vardenafil) or other PDE inhibitors (cilostazol) will not be allowed. Similarly, concomitant use of alpha-blockers, nitrates (GTN, ISMN, nicorandil) or direct vasodilators (hydralazine, naftidofuryl) will not be allowed. Use of anticoagulants or more than one antiplatelet agent will also be contraindicated. If a clinical need for these medications arises, the participant will be withdrawn from the study.

9.6. Post-study Treatment

The IMP will not be provided beyond the duration of the study.

10. SAFETY REPORTING

10.1. Definitions

Adverse Event (AE)	Any untoward medical occurrence in a participant to whom a medicinal product has been administered, including occurrences which are not necessarily caused by or related to that product.
Adverse Reaction (AR)	
An untoward and unintended response in a participant to an investigational medicinal product which is related to any dose administered to that participant.
 
The phrase "response to an investigational medicinal product" means that a causal relationship between a study medication and an AE is at least a reasonable possibility, i.e. the relationship cannot be ruled out.
 
All cases judged by either the reporting medically qualified professional or the Sponsor as having a reasonable suspected causal relationship to the study medication qualify as adverse reactions.

Serious Adverse Event (SAE)	
A serious adverse event is any untoward medical occurrence that:
 
 • results in death • is life-threatening • requires inpatient hospitalisation or prolongation of existing hospitalisation • results in persistent or significant disability/incapacity • consists of a congenital anomaly or birth defect. 
Other 'important medical events' may also be considered serious if they jeopardise the participant or require an intervention to prevent one of the above consequences.
 
NOTE: The term "life-threatening" in the definition of "serious" refers to an event in which the participant was at risk of death at the time of the event; it does not refer to an event which hypothetically might have caused death if it were more severe.

Serious Adverse Reaction (SAR)	An adverse event that is both serious and, in the opinion of the reporting Investigator, believed with reasonable probability to be due to one of the study treatments, based on the information provided.
Suspected Unexpected Serious Adverse Reaction (SUSAR)	
A serious adverse reaction, the nature and severity of which is not consistent with the information about the medicinal product in question set out:
 
 • in the case of a product with a marketing authorisation, in the summary of product characteristics (SmPC) for that product • in the case of any other investigational medicinal product, in the investigator's brochure (IB) relating to the study in question.

NB: to avoid confusion or misunderstanding of the difference between the terms “serious” and “severe”, the following note of clarification is provided: “Severe” is often used to describe intensity of a specific event, which may be of relatively minor medical significance. “Seriousness” is the regulatory definition supplied above.

Any pregnancy occurring during the clinical study and the outcome of the pregnancy should be recorded and followed up for congenital abnormality or birth defect, at which point it would fall within the definition of “serious”.

Safety data will be routinely collected at each follow-up, including clinical history of side effects or adverse events, clinical examination and blood tests (FBC, U+Es, LFTs). Patients will also be provided a telephone number to contact in case of side effects, and if the side effects suggest possible hypotension, may be asked to perform additional BP monitoring.

10.2. Causality

The relationship of each adverse event to the study medication must be determined by a medically qualified individual according to the following definitions:

Related: The adverse event follows a reasonable temporal sequence from study medication administration. It cannot reasonably be attributed to any other cause.

Not Related: The adverse event is probably produced by the participant’s clinical state or by other modes of therapy administered to the participant.

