11.4. Criteria for the Termination of the Study

A Data and Safety Monitoring Board will be established. They will review the data after 30 patients have been recruited to the study, or 12 months after the first visit of the first patient (whichever is sooner), or at the request of the sponsor or CI. If a decision to terminate the study is contemplated, this will be discussed with the CI and the sponsor prior to a final decision being made.

The advisory recruitment threshold is set at projected recruitment of <35 patients in 2 years, allowing for any delays resulting from the COVID-19 pandemic. No threshold is defined for efficacy for study cessation. Any statistically significant excess of SAEs in the treatment arm, or occurrence of unexpected treatment-related SAEs of sufficient severity (in the view of the DSMB), may also result in early cessation of the study. If after 12 months the recruitment falls below the rate expected to complete the study in 3 years, allowing for delays due to the COVID-19 outbreak, the overall study size can be reduced to 50 participants. Any data collected to that date, including on cilostazol, will be retained and analysed according to the original study plan. An interim statistical analysis plan will be signed off prior to the interim analyses.

11.5. Procedure for Accounting for Missing, Unused, and Spurious Data.

All physiological data will be reviewed and cleaned by automated and manual processes to reduce artefactual data. Data will be defined as artefactual or missing. The statistical analysis plan will describe the procedure for accounting for missing or spurious data. The completeness and correctness of the data will be monitored as per the monitoring plan

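### The protocol holds three conflicting causality standards, and the two mandatory classes in section 10.2 do not cover every event, so a suspected serious reaction could miss SAR or SUSAR status

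*Protocol*

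**What the plan says.** Protocol 10.1 (Definitions) sets the bar for an adverse reaction low: it is enough that "a causal relationship between a study medication and an AE is at least a reasonable possibility, i.e. the relationship cannot be ruled out". It also lets two parties make the call: "All cases judged by either the reporting medically qualified professional or the Sponsor as having a reasonable suspected causal relationship" qualify as adverse reactions.

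The SAR definition in the same section uses different words. The event must be serious and, in the reporting investigator's opinion, "believed with reasonable probability to be due to one of the study treatments". A SUSAR is then defined as "A serious adverse reaction, the nature and severity of which is not consistent with the information about the medicinal product in question", so SUSAR status depends on the SAR call.

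Protocol 10.2 (Causality) says that the relationship of each adverse event to the study medication "must be determined by a medically qualified individual according to the following definitions". Two classes follow. Related requires a reasonable temporal sequence and adds "It cannot reasonably be attributed to any other cause". Not Related requires that the participant's clinical state or another therapy is the probable cause.

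Three rules use the result. Protocol 10.3 ties follow-up to resolution or stability to events considered related. Protocol 10.6 gives expedited timelines (7 calendar days for fatal or life-threatening cases, 15 for others) to SUSARs only. Protocol 11.4, repeated in SAP 2.4, lists "occurrence of unexpected treatment-related SAEs of sufficient severity", as judged by the DSMB, among the reasons that may end the study early.

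**The concern.** A causality call is only as consistent as the threshold behind it. Here the general definition includes an event unless the drug can be excluded, while the operative classification excludes an event unless every other reasonable cause can be excluded. The SAR wording adds a third test, and that is the one that stands directly in front of SUSAR status.

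Two assessors who both follow the protocol could therefore class the same serious event differently. One who follows 10.2 to the letter would be compliant while leaving out a reaction that 10.1 counts, so monitoring against the protocol would not flag it. At stake are expedited reporting to the sponsor and the research ethics committee, the follow-up of related events, and what the DSMB sees labelled as treatment-related.

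**Working it through.** No arithmetic applies: the point depends on no rate, margin or sample size, and the plan states no figure to reproduce. The check is to take one serious, unexpected event with reasonable timing, vary only the strength of the rival cause, and read off each definition.

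| Case | Adverse reaction test, 10.1 | Class under 10.2 |
|---|---|---|
| (a) Drug possible, no other reasonable cause | Adverse reaction | Related |
| (b) Drug possible, another cause reasonable but not probable | Adverse reaction | Neither: fails Related because a rival cause is reasonable, fails Not Related because that cause is not probable |
| (c) Drug cannot be ruled out, another cause probable | Adverse reaction | Not Related |

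The definitions agree only in case (a). In case (b) the event has no class under 10.2. In case (c) the two sections contradict each other.

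The SAR wording does not settle (b) or (c). Reasonable probability is not quantified, and it is neither the adverse reaction test nor the 10.2 test. An investigator could find it met or not met in (b), and would more naturally find it not met in (c).

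The consequences, step by step:

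1. An assessor applying 10.2 does not class (b) or (c) as Related.
2. If that call is carried forward, the event is not treated as a SAR, and so cannot be a SUSAR under 10.1.
3. Expedited reporting in 10.6 is then not triggered.
4. Follow-up under the related-event rule in 10.3 does not apply unless the sponsor judges the event related.
5. The event does not carry the treatment-related label used in 11.4 and SAP 2.4.

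Protocol 10.3 requires any other suspect drug or device to be recorded, so the protocol itself foresees events with more than one candidate cause.

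**The case against.** The strongest reply is that much of the safety system does not use relatedness at all, and this is largely right.

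- All adverse events go on the CRF regardless of attribution (Protocol 10.3).
- SAEs, apart from protocol-defined exceptions, go to the DSMB within 24 hours with no causality condition (Protocol 10.4).
- The adverse event tables in SAP section 6 are not split by relatedness, and SAEs are listed in full.
- The statistical stopping limb in SAP 2.4 compares all SAEs by McNemar's test. The other limb rests on the judgement of a DSMB that receives SAEs whatever their label.
- A participant withdrawn for an adverse event is followed until it resolves or stabilises, whatever its cause (Protocol 8.9).
- The sponsor can class an event as an adverse reaction independently (Protocol 10.1).

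These safeguards rule out three stronger readings that a reader might infer. First, that such events would drop out of the counts: they would not. Second, that 10.2 makes every event with a rival cause Not Related: it does so only when the rival cause is probable, and otherwise leaves the event unclassified. Third, that most events in this population have another candidate cause and would be under-reported: vascular comorbidity makes rival causes likely in some participants, but the documents give no rate.

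What the reply does not remove is the exposure in labelling and expedited reporting. Notice to the DSMB is not notice to the research ethics committee. The sponsor's independent call is a weak backstop on the written text, because 10.4 routes SAEs to the DSMB without naming the sponsor. The sponsor's stated expedited route is the SUSAR report in 10.6, which comes after the causality call.

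**Conclusion.** The concern holds as an internal inconsistency in the safety definitions. There are three causality standards, one of them mandatory and stricter than the general definition, and the two mandatory classes are not exhaustive. The supportable consequence is that a suspected reaction could fail to reach SAR or SUSAR status. The text does not show that it would, since an assessor or the sponsor working from 10.1 could still classify it correctly.

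The size cannot be computed from the documents. For expedited reporting the affected set is limited to events that are serious, unexpected and have a competing explanation. For follow-up under 10.3 it is wider, because that rule is not restricted to serious events. Sample size, the primary comparison and the planned adverse event tables are unaffected.

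The conclusion assumes that 10.2 is used as the operative test, which its mandatory wording supports. The change should be made: the rule is wrong as written, although partly mitigated.

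**What to change.** Use one causality standard throughout the protocol:

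1. Keep the adverse reaction test of 10.1 (reasonable possibility, relationship not excluded) as the single threshold.
2. Put that test into the SAR definition in place of the reasonable-probability wording. Changing 10.2 alone would leave the wording that gates SUSARs untouched.
3. Define Related in 10.2 by the same test, and Not Related as its complement, so that every event falls into exactly one class.
4. Re-read any SAEs already classed under the current 10.2 wording against the single standard, preferably without knowledge of treatment, and report those whose status changes.

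This is a wording amendment plus a limited re-read. It needs no new data and no change to the analyses. The cost is that more events will be classed as related. There may also be a few more SUSAR reports, each of which can bring individual unblinding under 10.6, a small but real cost in a double-blind crossover.
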